 - c. Serum creatinine ≤1.5x institutional ULN. If creatinine is > 1.5 x ULN, patient is eligible if concurrent creatinine clearance ≥ 50 ml/min (≥ 0.05 L/min) (measured or calculated by CKD-EPI formula or Japanese version of CKD-EPI formula for Japanese patients).
 - d. ANC $\geq 1.0 \times 10^9 / L (\geq 1.0 \times 10^3 / \mu L, \geq 1,000 / mm^3)$
 - e. Platelets $\geq 100 \times 10^9 / L (\geq 100 \times 10^3 / \mu L, \geq 100 \times 10^3 / mm^3)$
 - f. Hemoglobin (Hb) \ge 8.5 g/dl, \ge 85 g/L, or \ge 5.3 mmol/L (without transfusion within previous week)
 - g. Phase Ia, and Phase 1b CRC cohort: Serum lipase ≤ 1.5 institutional ULN
 - h. Phase Ib PDAC cohort: Serum lipase >1.5 2.0 x ULN or asymptomatic >2.0 5.0 x ULN if related to PDAC
- 6. Recovery from any adverse events according to CTCAE v5.0 of previous anti-cancer therapies to baseline or CTCAE grade 1, except for alopecia CTCAE grade 2, sensory peripheral neuropathy CTCAE grade ≤ 2 or considered not clinically significant.
- 7. ECOG performance status ≤ 1
- 8. Life expectancy ≥ 3 months in the opinion of the investigator
- 9. Of legal adult age (according to local legislation) at screening.
- 10. Signed and dated written informed consent in accordance with ICH-GCP and local legislation prior to admission to the trial.
- 11. Male or female patients. Women of childbearing potential (WOCBP)¹ and men able to father a child must be ready and able to use highly effective methods of birth control per ICH M3 (R2) that result in a low failure rate of less than 1% per year when used consistently and correctly. A list of contraception methods meeting these criteria is provided in Section 4.2.2.3.

Permanent sterilisation methods include hysterectomy, bilateral salpingectomy and bilateral oophorectomy. Tubal ligation is NOT a method of permanent sterilisation.

A postmenopausal state is defined as no menses for 12 months without an alternative medical cause.

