7.8.2 Laboratory data

The analysis of laboratory data will be descriptively in nature and will follow standard procedures. The analysis of laboratory data will use the same "analyzing treatments" as described for AEs, except for that the baseline laboratory values will be included in the "on treatment" period. Patients having at least one post-baseline laboratory value will be displayed in the descriptive analyses. Patients with missing CTCAE grade at baseline or no baseline value but with post-baseline value will be displayed in the category "Missing CTCAE grade at baseline".

Descriptive statistics, including change from baseline, frequency of patients with transitions relative to the references range, will be provided for laboratory assessments at scheduled visits. Data collected during potential unscheduled laboratory assessments will be listed. No post-study laboratory values will be considered. CTCAE grade for applicable laboratory parameters will be calculated according to CTCAE v5.0. The following outputs will be presented:

- Baseline, last value and difference from baseline
- Worst CTCAE grade experienced during the on-treatment period

- Transitions of the CTCAE grade from baseline to the worst lab values, from baseline to the last lab values, and from the worst to last values during the on-treatment period
- Possible clinically significant laboratory values
- Transitions for laboratory values without CTCAE grade based on reference ranges

Note: For calculating the change in CTCAE grade from baseline, patients with a CTCAE grade of -9 (no CTCAE grade defined) or CTCAE grade of -5 (overlapping reference ranges) will be treated as a CTCAE grade 0 for all analyses. In laboratory listings, the CTCAE grade is displayed as -9 and -5, respectively.

For Uric Acid, Hypokalemia, amylase, bicarbonate, eosinophils, glucose (high direction), INR of prothrombin time, lipase, methemoglobin, sodium (low direction) the CTCAE grade cannot always be assigned by the laboratory parameter itself as two different CTCAE grades have the same laboratory constellation, but are distinguished by additional clinical parameter. In this case a CTCAE grade of -1 will be assigned. These will not be considered for laboratory analyses. In laboratory listings, the CTCAE grade is displayed as -1, respectively.

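### SAP 7.8.2 leaves laboratory values coded CTCAE grade -1 out of the graded tables, so a patient's worst on-treatment grade can be lowered but never raised, and an abnormal patient can be shown as grade 0

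*SAP*

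**What the plan says.** SAP section 7.8.2 names ten parameters: uric acid, hypokalemia, amylase, bicarbonate, eosinophils, high glucose, INR, lipase, methemoglobin and low sodium. For these, "the CTCAE grade cannot always be assigned by the laboratory parameter itself", because two grades share the same laboratory result and only clinical information separates them. The rule is: "In this case a CTCAE grade of -1 will be assigned. These will not be considered for laboratory analyses". Listings still show the value with code -1.

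Four other provisions in the same section matter here:

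- The treatment periods are those used for adverse events, "except for that the baseline laboratory values will be included in the" on-treatment period.
- The planned outputs include "Worst CTCAE grade experienced during the on-treatment period", grade transitions between baseline, worst and last values, and "Possible clinically significant laboratory values".
- Codes -9 and -5 have a different rule for the change in grade from baseline: they "will be treated as a CTCAE grade 0 for all analyses".
- A missing baseline grade has its own place in the tables: "Patients with missing CTCAE grade at baseline or no baseline value but with post-baseline value will be displayed in the category" for a missing baseline grade.

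No table category, count or bounding rule is given for code -1.

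**The concern.** A -1 value is abnormal; only its grade is open. Codes -9 and -5 and a missing baseline grade all keep a place in the tables, but a -1 value has none, and the patient's other values stand in for it. Because any patient with a post-baseline value is displayed and baseline counts as on treatment, the stand-in can be a normal baseline. A reader of the worst-grade table would then see no graded abnormality where one was measured.

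Eight of the ten parameters are in the protocol's safety panel (protocol section 5.2.3). Bicarbonate and methemoglobin are not, and amylase is measured in phase Ib only. Protocol section 1.4 lists a rise in lipase or amylase among the adverse events that might be expected from the mode of action, so the parameters are not peripheral.

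**Working it through.** The documents give no figure on this point, so the check is of the rule itself.

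**Inputs** (all SAP 7.8.2): ambiguous values are dropped; the output is the worst on-treatment grade; baseline is included; every patient with a post-baseline value is displayed.

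**Direction.** Let A be all of a patient's values for one parameter, baseline included, and S the values with a definite grade. S is part of A. The grade shown is max(S) and the actual worst grade is max(A), so max(S) ≤ max(A). Dropping -1 values cannot raise the worst grade.

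**Cases** (the actual grade behind each -1 is supposed for illustration):

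| Definite grades | Value coded -1 is really | Actual worst | Shown worst |
|---|---|---|---|
| 0 (baseline) | 3 | 3 | 0 |
| 2 | 3 | 3 | 2 |
| 3 | 2 | 3 | 3 |
| none | 3 | 3 | not defined |

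The first row gives the grade 0 result. It arises because a grade 0 baseline is the only graded value left; code -1 itself is not converted to 0. On the fourth row the SAP does not say how the patient is shown.

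**Transition tables.** No single direction follows. If the last value is coded -1, the last grade can move either way. If the baseline is coded -1, the SAP does not say whether it is dropped or falls under the missing-baseline-grade category.

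**Outputs not based on grade.** Read literally, the exclusion covers all laboratory analyses. On the natural reading it concerns the graded ones, and the values stay in change from baseline, reference-range transitions and possibly significant values. The text does not settle this.

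**Size.** The frequency of -1 values is not in the documents, so the number of patients affected cannot be computed. For scale only, one hypothetical patient is 1/8 = 12.5 percentage points of a phase Ia dose group of 8 (protocol section 1.2 reports groups of that size), or 1/48 = 2.1 points of the 48 phase Ia patients. Under protocol version 7.0, laboratory results of ongoing patients are no longer collected in the eCRF, so the rule acts on earlier data only.

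**The case against.** The strongest reply is that this is a disclosed convention with a stated reason. The SAP names the parameters, explains why no grade can be derived from the result alone, and keeps the values in the listings. Setting -1 to grade 0, as is done for -9 and -5, would be worse. The sponsor's laboratory guide cited in SAP section 8 may already flag these values, and it was not available to check. This stands as a reason to rate the point low. It does not put the values back into the graded tables as the SAP is written.

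The safety consequences are also limited. ALT, AST, bilirubin, creatinine, neutrophils and platelets are not among the ten parameters. Clinically relevant abnormal findings are reported as adverse events (protocol section 5.2.3) and tabulated by highest CTCAE grade (SAP section 7.8.1), although that route depends on the investigator's judgement.

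A reader might infer more than the documents support:

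- *That a pancreatic signal is being hidden.* Protocol section 1.4 reports that the Safety Monitoring Committee, with data up to 3.6 mg/kg, saw no pattern of anticipated adverse events except infusion-related reactions. The most common grade 3 events in protocol section 1.2 do not include lipase or amylase.
- *That lipase baselines were grade 0 because entry was restricted.* The criterion is "Phase Ia, and Phase 1b CRC cohort: Serum lipase ≤ 1.5 institutional ULN", which admits values above the upper limit of normal.
- *That the transition tables are biased in a known direction, with a screening grade replacing a -1 baseline.* The imputation rule in protocol section 7.5 covers missing laboratory values. A -1 baseline has a value and lacks only a grade.
- *That the frequency of lowering can be obtained by counting hypothetical grade patterns.* Such counts depend on whether the lower or the higher candidate grade is assumed. They show direction only.

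**Conclusion.** The point holds as a limited defect of display. Under SAP 7.8.2 as written, a patient's worst on-treatment grade for the ten parameters can be understated and cannot be overstated, and a patient with a grade 0 baseline and only -1 values afterwards appears as grade 0 despite an abnormal result. This rests on two assumptions: that both candidate grades behind a -1 code are at least grade 1, and that the unavailable laboratory guide adds no further display rule.

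The number of patients affected is unknown and may be zero. SAP section 4 names primary and secondary endpoint analyses for the abbreviated report and does not say whether the graded laboratory tables will be in it. The documents do not support a claim that safety reporting as a whole is biased. Clarifying the rule is a worthwhile improvement, not a necessary correction.

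**What to change.** In SAP 7.8.2, replace the second sentence of the -1 rule with:

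> No numeric grade is derived for these values. In the worst-grade and transition tables, a patient with no definite post-baseline grade above 0 and at least one post-baseline value coded -1, who would otherwise appear as grade 0 or without a grade, is shown in one category: *abnormal, grade not determinable*. Other patients stay at their worst definite grade, and a footnote gives the number who also have a -1 value. A baseline coded -1 is shown in the existing category for a missing baseline grade. The underlying values are kept in all value-based outputs: change from baseline, reference range, and possible clinically significant values.

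This assigns no grade that the data cannot support, and it settles how to show a patient with no definite grade at all. It needs no new data, no matching to adverse event records and no clinical rule. The cost is one extra table row, a footnote, and a small deviation from the sponsor's standard laboratory programming. If no -1 values occur, the tables do not change.

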7.8.3 Vital signs

Vital signs and physical examination, at Screening, baseline, during the course of the trial and at the end-of-trial evaluation will be listed with regard to possible changes compared to findings before start of treatment.

7.8.4 ECG

ECG data will be collected as described in CTP Section 5.2.4. Clinically significant findings in ECG data will be reported under "Adverse events" if applicable and will be analyzed accordingly. In addition, patients ECG assessments will be listed for all time points.

7.8.5 Others

Details on interim analysis are described in section 7.4 in CTP as follows.

No formal interim analysis is planned for PK and immunogenicity. Preliminary, exploratory analysis of PK and if applicable of immunogenicity will be performed prior to database lock during study conduct based on all evaluable data at the time of analysis. This will be performed to support dose escalations and e.g. in case the information is needed to inform other activities during the development of substance such as concomitant treatment restrictions in other trials. In contrast to the final calculations, the preliminary, exploratory analysis will be based on planned sampling times rather than on actual times, regardless of whether actual times were within the time windows or not. Therefore, minor deviations of preliminary and final results may occur. No formal preliminary PK and immunogenicity report will be written.

In Phase 1b there will be a continuous monitoring of the efficacy in terms of PFS4 and OR (and PD-modulation). Tumor marker (CEA, CA19-9) modulations will be monitored continuously. An arm may be terminated early due to lack of efficacy.

10. HISTORY TABLE

Table 10: 1 History table

Version	Date (DD-MMM-YY)	Author	Sections changed	Brief description of change
Initial	09-SEP-22		None	This is the initial TSAP with necessary information for trial conduct
Version 1	03-NOV-22		2, 4, 5.3, 5.4.1, 5.4.2, 5.4.3, 6.1-4, 6.6, 7, 7.3, 7.5.2, 7.5.3, 7.6, 7.8.1, 7.8.5, 9.1	TSAP updated according to comments and feedback during review period.
Version 1.1	09-OCT-2023		7.4,7.5,7.6	Align sections 7.4,7.5,7.6 heading titles with version 4 TSAP template as applicable.
Final	30-NOV-2023		2, 5.3, 5.4, 5.4.2, 7.4.1, 7.5.2, 7.8.1 and 7.8.2.	TSAP updated according to final comments.
